2.6 Safety Data

2.6.1 Adverse Events

All AEs will be coded using MedDRA Version 22.1 for consistency with the Study 812P306 AE analyses. Study-level Lower Level Terms (LLT) will be assigned to the corresponding PT and SOC in MedDRA Version 22.1.

2.6.2 Prior and Concomitant Medications

A concomitant treatment refers to all treatment, including concomitant therapies as well as herbal treatments, vitamins, behavioral treatment, and non-pharmacological treatment, such as psychotherapy, taken between the dates of the first dose of study drug and the end of the subject's participation in the study (Visit 22/EOS), inclusive.

CONFIDENTIAL

Treatments that started prior to the first dose of study drug are considered prior treatments whether or not they were stopped prior to the first dose of study drug. Any treatment starting on or after the first dose of study drug will be considered as concomitant. If a treatment starts prior to the first dose of study drug and continues after the first dose of study drug, the medication will be considered both prior and concomitant.

Prior and concomitant medications will be coded using World Health Organization Drug Dictionary (WHO-DD Enhanced version September 2019), Anatomical Therapeutic Chemical (ATC) level 4 for ATC class and level 5 (clinical substance) for preferred name (PN).

2.6.3 Laboratory Evaluations

Laboratory tests will include hematology, serum chemistry, and urinalysis. Values will be presented using the international system of units (SI).

Hematology:

Hematology parameters will include complete blood count (CBC), white blood cell count with differential, platelet count, red blood cell (RBC) count, hemoglobin, and hematocrit.

Serum Chemistry:

Serum chemistry parameters will include albumin, alanine aminotransferase (ALT), aspartate aminotransferase (AST), alkaline phosphatase (ALP), bicarbonate, bilirubin (direct), bilirubin (total), blood urea/blood urea nitrogen (BUN), calcium, chloride, creatinine, phosphate, potassium, sodium, total protein, and glucose.

Urinalysis:

Urinalysis parameters will include bilirubin, glucose, ketones, nitrites, occult blood, pH, protein, specific gravity, urobilinogen, and WBCs.

Other:

Serology, follicle stimulating hormone (FSH), serum drug screen results, standard urine drug screen results, point of care urine drug screen results, and pregnancy test results will be listed separately.

2.6.4 Vital Signs

Vital signs data will include weight (kg), BMI (kg/m²), systolic blood pressure (mmHg), diastolic blood pressure (mmHg), heart rate (beats per minute), respiratory rate (breaths per minute) and temperature (°C). Blood pressure and heart rate measurements taken in the standing and the seated position will be analyzed.

2.6.5 Electrocardiogram

The ECG parameters to be summarized include heart rate, PR interval (msec), QRS interval (msec), QT interval (msec), and QT interval corrected for heart rate using Fridericia's (QTcF) correction formula.

3 STATISTICAL METHODS

3.1 General Methods

Premier Research, the designated CRO, will perform all statistical analysis using SAS version 9.4 or higher. Premier Research will be responsible for creating table, listing, and figure reports by SAS programming and delivering the reports, as well as the programs, to Supernus at study completion.

All analyses will be based on subjects who received any amount of study drug in Study 812P311. This will be referred to as the Safety Population. Since subjects received variable dosing in this study, all subject data will be summarized together under All SPN-812.

For categorical variables, summary statistics will include the number and percentage of subjects within each category (with a category for missing data). Percentages will be based on the total number of subjects with non-missing data. For continuous variables, summary statistics will include the number of non-missing observations, mean, standard deviation (SD), median, and interquartile range (Q1, Q3), minimum, maximum.

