# 2. STUDY OBJECTIVES AND ENDPOINTS

#### 2.1. Primary Safety Objective:

To monitor and collect long-term safety data on the use of SPN-812 as monotherapy for the treatment of ADHD in the adult population.

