## 2.2. Secondary Efficacy Objective

To evaluate the efficacy of SPN-812 as monotherapy for the treatment of ADHD in the adult population.

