On a case-by-case basis, a subject who did not complete Study 812P306 (e.g., randomized, dosed SM and had at least one post-baseline AISRS assessment and then early terminated) may be allowed to screen and, if eligible, enroll in Study 812P311, but only after receiving approval from the Site Investigator, Medical Monitor, and the Sponsor. For these subjects, use **INCLUSION/EXCLUSION CRITERIA 'B'** (Section 3.3.3.) and follow **SCHEDULE 'B'** (Table 2; Figure 2).

All subjects will initiate SPN-812 dosing at 200 mg/day once daily (QD) during the first 2 weeks of the study. At Visit 2 and all subsequent study visits, per the Investigator's discretion and based on Investigator's assessment of the subject's clinical response and tolerability, the dose of SPN-812 can be titrated up or tapered down in increments of 50 mg/day, 100 mg/day, 150 mg/day, or 200 mg/day per week to a target dose within the ranges between 200 and 600 mg/day. Additionally, after the first 12 weeks of dosing (after Visit 4), at the discretion of the Investigator and based on the subject's clinical

response, the optimized dose of SPN-812 may be supplemented with an adjunctive FDA-approved stimulant treatment (see Section 4.3.).

Following the day that the subject takes first dose of SPN-812 (Day 1), the subject will have a study visit every 2 weeks for the first 4 weeks of the study (Visit 2 and Visit 3). After Visit 3, study visits (Visits 4-22) will occur 12, 20, 28, 36, 44, 52, 60, 68, 76, 84, 92, 100, 108, 116, 124, 132, 140, 148 and 156 weeks after first dose of SPN-812 (approximately every 8 weeks). A Point of Care (POC) urine drug screen (Test 1 and 2) will be completed at Visits 1, 6, 8, 10, 12, 14, 16, 18, and 20 (Table 3). In addition, the site should conduct a follow-up phone call (FPC) with each subject 4 weeks after Study Visits 3 thru Visit 21 to assess adverse events, changes in concomitant medications and obtain results of home pregnancy test (FOCP only). Subjects will also be contacted for final safety follow-up (FPC) approximately 1 week after the End of Study (EOS) visit.

The timing of Study Visits 2-22 and FPCs should occur per the Schedule of Events and Assessments (**SCHEDULE 'A'** [Table 1] or **SCHEDULE 'B'** [Table 2]) by day of study relative to the date of subject's first dose of SPN-812.

Note: The same assessments/procedures are performed at Study Visits 2-22 between **SCHEDULE 'A'** and **SCHEDULE 'B'**.

[figure not shown]

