### 4.3. Adjunctive Stimulant Therapy

If after 12 weeks of dosing SPN-812 (Visit 4) the Site Investigator determines that administration of the optimized dose of SPN-812 is not eliciting an adequate clinical response, the Site Investigator may consider supplementing SPN-812 therapy with an adjunctive FDA -approved stimulant for use in ADHD [e.g., Vyvanse® (lisdexamfetamine dimesylate), Concerta® (methylphenidate)]. Adjunctive stimulant therapy should be initiated at the lowest recommended daily dose, and the dosing and safety management guidelines provided in the prescribing information for the stimulant must be followed.

Dose adjustment for the stimulant as well as evaluation of clinical response will be at the Investigator's discretion. Regardless of the dose of stimulant administered, the subject must continue to receive SPN-812 at the optimized dose determined per the study protocol. Subjects with known previous allergic reactions to either methylphenidate or amphetamine or other ingredients found in those dosage forms are not eligible for concomitant stimulant therapy. Adjunctive stimulant therapy should be carefully documented.

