### 4.7. Concomitant Medications

SPN-812 is a strong CYP1A2 inhibitor. Substrates with a narrow therapeutic window are prohibited during the study. Specific prohibited concomitant medications for this study include known CYP1A2 substrates (e.g., theophylline, melatonin).

Subjects who follow **SCHEDULE 'B'** and are taking any prohibited medications at screening (e.g., ADHD medications) should discontinue use (washout) at least 7 days prior to first dose of OLE SM.

No concomitant medications are allowed during the study, with the following exceptions:

- Nutritional supplements (e.g., multivitamins, fish oil) (herbal supplements are prohibited)
- EMLA® or other numbing cream for venipuncture
- Common over-the-counter therapies for minor transient ailments (e.g., acetaminophen for headache, ibuprofen for fever).
- Following the first 12 Weeks of dosing OLE SM, subjects may supplement SPN-812 with an adjunctive FDA approved stimulant for use in ADHD [e.g., Vyvanse® (lisdexamfetamine dimesylate), Concerta® (methylphenidate)] (See Section 4.3.).

All concomitant medications will be recorded in the eCRF, including Adjunctive Stimulant Therapy (carefully document reason for use).

Caffeine use is permitted during the study and will be recorded in the eCRF.

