# 7.8. Efficacy Analysis

The efficacy analysis will be based on the safety population. Each efficacy endpoint will be listed and summarized descriptively by group of the optimized dose, if applicable. In addition, if applicable, subjects who received adjunctive stimulant therapy will be identified by flagging for categorical summary. Total and subscale scores/points for AISRS, CGI-S, CGI-I, GAD-7, BRIEF-A, SDQ, and AAQoL will be summarized by optimized dose (if applicable) and visit and will be examined. Baseline will be defined for all subjects as the last non-missing value prior to SPN-812 dosing in Study 812P311.

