### 7.9. Safety Analysis

Safety analyses will be performed by optimized dose group and overall based on the Safety Population.

The incidence rate of AEs will be calculated for each system organ class (SOC) and preferred term (PT). The severity of the AEs and the relationship to SM will be summarized for each SOC and PT.

AEs will be summarized using discrete summaries at the subject and event level by SOC and PT, and by severity and relationship separately. Verbatim description and Medical Dictionary for Regulatory Activities (MedDRA) SOCs and PTs for all AEs will be contained in the subject data listings.

Clinical laboratory values will be summarized by visit by optimized dose group and overall using descriptive statistics. For quantitative laboratory parameters, both actual values and change from baseline values will be summarized.

Vital signs will be summarized by visit by optimized dose group and overall using descriptive statistics. Both actual values and change from baseline will be summarized.

ECG results will be summarized by visit by optimized dose group and overall using descriptive statistics (for quantitative ECG parameters) and frequency tables (for qualitative ECG parameters, including the overall ECG finding).

C-SSRS outcomes will be summarized using number and percent of subjects by categories for suicidal ideation only, suicidal behavior only and suicidality (ideation and behavior combined). The summary will be presented by optimized dose group and overall.

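### Both objectives concern SPN-812 as monotherapy, but no planned SAP summary visibly separates data before and after an added stimulant

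*SAP*

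**What the plan says.** The primary objective (protocol section 2.1) is: "To monitor and collect long-term safety data on the use of SPN-812 as monotherapy for the treatment of ADHD in the adult population". The secondary objective (section 2.2) is: "To evaluate the efficacy of SPN-812 as monotherapy for the treatment of ADHD in the adult population".

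The design then allows a second ADHD drug. Protocol section 3.1 permits an approved stimulant "after the first 12 weeks of dosing (after Visit 4), at the discretion of the Investigator". Section 4.3 ties it to outcome: if the optimized dose "is not eliciting an adequate clinical response, the Site Investigator may consider supplementing SPN-812 therapy with an adjunctive" stimulant. Section 4.7 requires stimulant use and the reason for it to be recorded in the eCRF.

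On analysis, protocol section 7.8 (efficacy) plans that "if applicable, subjects who received adjunctive stimulant therapy will be identified by flagging for categorical summary". Section 7.9 has no counterpart: "Safety analyses will be performed by optimized dose group and overall based on the Safety Population". Section 7.1 gives precedence to the methods that the SAP describes.

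SAP section 3.1 pools: "Since subjects received variable dosing in this study, all subject data will be summarized together under All SPN-812". The SAP's efficacy section (4.4), its safety sections (4.5 to 4.5.8) and its lists of tables, listings and figures do not mention stimulant or adjunctive therapy. The splits it lists, by age group and by actual dose, apply to exposure and planned dose only. Stimulants would surface as entries in the concomitant-medication table (Table 2.3, by ATC class and preferred name) and in Listing 2.2.

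**The concern.** The objectives name one regimen, while the planned long-term summaries can contain two. Variable dosing is a reason not to tabulate by dose. It does not address subjects who take another ADHD drug as well.

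For efficacy the mixing depends on outcome. Stimulants go to subjects judged to respond inadequately to SPN-812, so from Visit 5 a by-visit mean or responder rate may replace poor monotherapy scores with scores on combination therapy.

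For safety, which is the primary objective, a cumulative count does not show whether an event began before or after the stimulant was added. The protocol's own lists overlap. Section 1.1 names decreased appetite, sleep problems and headaches for stimulants. Section 1.2.2 names decreased appetite, headache and insomnia among the commonest events in adults on the immediate-release form.

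The study is single-arm and descriptive, so causal attribution is not the issue. The issue is which regimen a row describes.

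**Working it through.** **Which planned results can mix regimens.** The documents give no sample-size or power figure to reproduce, so the first step compares the schedule with the SAP outputs.

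- Cumulative safety: TEAEs (SAP 4.5.1), potentially clinically significant laboratory values (4.5.3.1), vital-sign abnormalities (4.5.4), ECG abnormalities (4.5.5), and C-SSRS responses at any visit (4.5.6). These run from first dose to the end and have no cut at stimulant start.
- By-visit safety at Visits 5-22: Tables 5.1.2, 5.2.2, 5.4, 6.1, 7.1, 7.2, 8 and 9, for whichever of these visits each assessment is scheduled.
- By-visit efficacy at Visits 5-22: Tables 11.1 to 11.11 and Figures 1 to 7.
- Not affected: rows through Visit 4, because a stimulant is allowed only after that visit.

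**How much of the schedule is open to mixing.** Protocol section 3.1 places Visits 2 and 3 at Weeks 2 and 4, and Visits 4 to 22 every 8 weeks from Week 12 to Week 156.

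- Post-baseline visits: 2 + 19 = 21. Visits 5-22: 18. Share: 18/21 = 85.7%.
- Weeks after Week 12: 156 - 12 = 144. Share: 144/156 = 92.3%.

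These are nominal. Section 3.4 lets subjects continue past Visit 22, and participation may end earlier once the product is approved and available.

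**Patient-time after stimulant start.** Let u be the fraction who start, s the mean start week, and assume everyone stays 156 weeks. Then share = u × (156 - s) / 156. The documents give neither u nor s. The range of 5-30% for u is an assumption: 366 × 0.05 ≈ 18 subjects and 366 × 0.30 ≈ 110.

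| Assumed start | u = 0 | u = 5% | u = 30% |
|---|---|---|---|
| All at Week 12 | 0% | 0.05 × 144/156 = 4.6% | 0.30 × 144/156 = 27.7% |
| Mean Week 84 | 0% | 0.05 × 72/156 = 2.3% | 0.30 × 72/156 = 13.8% |

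Week 12 is the earliest permitted time, so the first row gives the highest share for that uptake and retention. Starts averaging the midpoint of the remaining time (Week 84) halve it. Different dropout between starters and non-starters would change these shares.

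**Does the protocol's flag close the gap?** It is conditional, sits only in the efficacy section, and defines neither a monotherapy subset nor a cut at stimulant start. Restoring it would identify users but would not by itself produce a monotherapy summary, and it would leave safety untouched.

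**The case against.** The case for leaving the plan alone has weight.

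- **The flag may survive.** Section 7.1 replaces only methods that the SAP describes, and the SAP is silent here. The table shells (SAP Appendix B) were not available, so a column or footnote for stimulant users could exist. This stands, and it limits confidence in the omission to moderate.
- **Part of the tension is in the protocol.** The design itself permits adjunctive therapy, and section 7.9 never promised a safety split. A whole-cohort table is a legitimate main display. This also stands, and the pooled column should stay.
- **The data are recoverable.** Stimulant use and reason are recorded, and medications are listed by subject. True, but a split chosen after the results are seen is not prespecified.
- **The adverse-event overlap is thin.** The insomnia observation comes from 26 adults on an immediate-release form given three times daily. Section 1.2.1 names somnolence and headache as commonest in healthy adults. The overlap is a reason to show timing, not evidence of confounding.

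A reader might infer that the SAP deliberately merges the two regimens, that the long-term results are distorted by a known amount, or that nothing in the outputs describes monotherapy. The documents support none of these. The reason given for pooling concerns dose, uptake is not stated and could be zero, and rows through Visit 4 are monotherapy.

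**Conclusion.** The gap is real and worth fixing, with moderate confidence. As far as the available SAP shows, the long-term part of both monotherapy objectives would not be reported separately once any subject adds a stimulant. The protocol's efficacy flag is not visible in the SAP, and neither document plans a safety split.

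The size cannot be fixed from the documents. Under the assumptions of 5-30% uptake and no dropout, between 2.3% and 27.7% of patient-time follows stimulant start, depending on timing. At zero uptake the pooled tables are monotherapy tables. The conclusion would weaken if the shells already carry a stimulant split. In that case the SAP text should say so.

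**What to change.** In SAP sections 3.1, 4.4 and 4.5:

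1. Carry forward the protocol 7.8 flag, derive the first stimulant date from the eCRF, and report the number and timing of starts. Keep the All SPN-812 column.
2. Beside it, for the safety tables listed above, add two summaries.
   - **Before stimulant:** from first open-label dose up to the first stimulant dose or, if there is none, to the end of safety follow-up. Assessments made at the visit where the stimulant is prescribed, before its first dose, belong here. Otherwise the score that prompted the stimulant would drop out of the monotherapy column.
   - **On or after first stimulant start:** labelled as including any time after the stimulant is stopped.
3. Assign TEAEs by onset date and count a subject once per preferred term within each period.
4. Split the SAP 4.3 exposure at the stimulant date. With first dose F, last dose L and stimulant start S (S not after L), the periods are S - F and L - S + 1 days, which sum to the SAP's L - F + 1.
5. State a rule for unclear order. Protocol 7.2 imputes partial dates but SAP 3.3 allows no imputation. Count such events as before stimulant, the conservative choice for monotherapy, and report how many there are.
6. For by-visit efficacy, show all data and before-stimulant data side by side, and state that the latter is selected by outcome and so favours monotherapy.
7. For responder rates, add a row that counts starters as monotherapy non-responders only at visits after stimulant start, using the same observed-data denominator as the all-data row at that visit.

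The cost is SAP wording, one derived date, a period variable and extra columns, with no new data collection. The downsides are wider tables, selection by outcome in the before-stimulant column, and smaller late numbers: once all assumed starters have begun, 366 - 18 = 348 down to 366 - 110 = 256 before dropout. Carrying the flag alone would be cheaper but would leave the primary safety objective without a monotherapy summary.

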All subjects will initiate SPN-812 dosing at 200 mg once daily (QD) during the first 2 weeks of the study. At Visit 2 (Week 2) and all subsequent study visits, per the Investigator's discretion based on the subject's clinical response and tolerability, the dose of SPN-812 can be titrated up or tapered down in increments of 50 mg/day, 100 mg/day, 150 mg/day, or 200 mg/day per week to a target dose within the ranges between 200 and 600 mg/day. Additionally, after the first 12 weeks of dosing (after Visit 4), at the discretion of the Investigator and based on the subject's clinical response, the optimized dose of SPN-812 may be supplemented with an adjunctive FDA-approved stimulant treatment (see Section 4.3. ).

Following the day that the subject takes first dose of SPN-812 (Day 1), the subject will have a study visit every 2 weeks for the first 4 weeks of the study (Visit 2 and Visit 3). After Visit 3, study visits (Visits 4-22) will occur 12, 20, 28, 36, 44, 52, 60, 68, 76, 84, 92, 100, 108, 116, 124, 132, 140, 148 and 156 weeks after first dose of SPN-812 (approximately every 8 weeks). In addition, the site should conduct a follow-up phone call (FPC) to each subject 4 weeks after Study Visits 3-21 to assess adverse events, changes in concomitant medications, obtain results of home pregnancy test (FOCP only). The timing of each study visit (V2-V22) and each FPCs should occur per the Schedule of Events and Assessments (Table 1 [SCHEDULE 'A'] or Table 2 [SCHEDULE 'B']) relative to the date of subject's first dose of SPN-812.

Subjects will be contacted for a final safety follow-up (FPC) approximately 1 week after the EOS visit. The clinical course of each AE should be followed for at least 30 days following the date of last dose of SM (due to either EOS or ET) or until resolution, or until, in the medical judgment of the Investigator, the event has stabilized or is assessed as chronic.

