## 1.3. Study Rationale

The pharmacological similarity of viloxazine to other agents with proven efficacy in ADHD provides the rationale for a clinical trial to test its long-term effectiveness and safety in this indication. The effectiveness and safety of SPN-812 has been demonstrated in the 812P201 study, the change from baseline in CAARS total score at end of study (EOS) was significantly reduced with SPN-812 IR 150 to 300 mg/day compared to placebo in adults (ages ≥ 18 years of age) with ADHD. The efficacy and safety of SPN-812 showed positive results in three separate trials that assessed the effects of 200 mg/day and two separate trials assessing the effects of 400 mg/day. The proposed doses of 200 to 600 mg/day SPN-812 in the current open label extension study (812P311) and the previous randomized, double-blind, placebo-controlled study (812P306) are expected to provide similar exposure in adults compared to that provided by 200 to 400 mg/day in children and adolescents. This dose range was used in previous Phase I (single and multiple dose) studies where a low number of AEs were observed, and those AEs that were observed were mild to moderate in severity. This Open-Label Extension (OLE) study will determine the additional long-term safety and efficacy of SPN-812 in adult patients with ADHD among eligible subjects that have completed 812P306.

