1 INTRODUCTION

Study 812P311 is an open-label extension (OLE), long-term, multicenter, flexible-dose study of SPN-812 in adults diagnosed with Attention-Deficit/Hyperactivity Disorder (ADHD). Up to 366 subjects will be enrolled. Subjects who have completed Study 812P306 (a randomized, double-blind, placebo-controlled study of SPN-812 for the treatment of ADHD) will be eligible for enrollment into Study 812P311. Interest and suitability will be ascertained at the last 1 to 2 visits of 812P306 to allow immediate enrollment into Study 812P311 for subjects who complete Study 812P306

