5.1 List of Tables

Number	Title
Table 1.1	Subject Disposition – All Subjects
Table 1.2	Protocol Deviations and Violations – All Subjects
Table 2.1	Demographic and Baseline Characteristics - Safety Population
Table 2.2	Prior Medications by ATC Class Level 4 and Preferred Name - Safety Population
Table 2.3	Concomitant Medications by ATC Class Level 4 and Preferred Name – Safety Population
Table 2.4	Medical History by System Organ Class and Preferred Term – Safety Population
Table 3.1	Study Drug Exposure by Age Group - Safety Population
Table 3.2	Planned Doses by Study Visit and Age Group - Safety Population
Table 3.3	Study Drug Exposure by Age Group and Actual Dose - Safety Population
Table 4.1	Overview of Treatment-emergent Adverse Events - Safety Population
Table 4.2	Treatment-emergent Adverse Events by System Organ Class and Preferred Term - Safety Population
Table 4.3	Treatment-emergent Adverse Events Occurring in at Least 5% of Subjects by Preferred Term - Safety Population
Table 4.4	Treatment-emergent Adverse Events by System Organ Class, Preferred Term, and Maximum Severity - Safety Population
Table 4.5	Treatment-emergent Adverse Events by System Organ Class, Preferred Term, and Relationship to Study Drug - Safety Population
Table 4.6	Serious Treatment-emergent Adverse Events by System Organ Class and Preferred Term - Safety Population
Table 4.7	Treatment-emergent Adverse Events Leading to Study Drug Discontinuation by System Organ Class and Preferred Term - Safety Population
Table 4.8	Treatment-emergent Adverse Events of Special Interest by System Organ Class and Preferred Term - Safety Population
Table 5.1.1	Subjects with Potentially Clinically Significant Post-Baseline Hematology Results – Safety Population
Table 5.1.2	Change from Baseline in Hematology Parameters by Study Visit – Safety Population
Table 5.2.1	Subjects with Potentially Clinically Significant Post-Baseline Chemistry Results – Safety Population
Table 5.2.2	Change from Baseline in Chemistry Parameters by Study Visit – Safety Population
Table 5.3	Subjects with Abnormal Liver Enzymes and Liver Function Tests – Safety Population
Table 5.4	Change from Baseline in Urinalysis Parameters by Study Visit – Safety Population
Table 6.1	Vital Signs by Study Visit – Safety Population

Supernus Pharmaceuticals, Inc. CONFIDENTIAL

Number	Title
Table 6.2	Subjects with Abnormalities in Vital Signs Parameters - Safety Population
Table 7.1	12-Lead Electrocardiogram by Study Visit – Safety Population

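### SAP 3.1 pools all subjects in one column regardless of 812P306 treatment, so adverse event percentages mix first exposure with continued use and safety changes mix on-drug with drug-free baselines

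*SAP*

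**What the plan says.** **Who enters.** The SAP Introduction describes 812P306 as "a randomized, double-blind, placebo-controlled study of SPN-812 for the treatment of ADHD", so rollovers come from both arms. Protocol 3.1 also admits delayed rollovers (more than 7 days after the last 812P306 visit), 812P306 early terminators case by case, and de novo subjects once a Note To File has IRB approval. These last three follow Schedule B.

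**Dose at entry.** Protocol 3.1: "All subjects will initiate SPN-812 dosing at 200 mg/day once daily (QD) during the first 2 weeks of the study". Protocol 1.3 gives one dose range for both studies: "200 to 600 mg/day SPN-812 in the current open label extension study (812P311) and the previous randomized, double-blind, placebo-controlled study (812P306".

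**Pooling.** SAP 3.1: "Since subjects received variable dosing in this study, all subject data will be summarized together under All SPN-812". Variable dosing is the only reason given. In SAP 5.1 only exposure Tables 3.1 to 3.3 are split, by age group and, in Table 3.3, by dose as well: "Study Drug Exposure by Age Group and Actual Dose - Safety Population". Protocol 7.9 groups safety results by optimized dose and overall, again not by prior treatment, and Protocol 7.1 lets the SAP supersede.

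**Counting events.** Protocol 5.1.1 and 6.3.3 record events before the first extension dose as medical history. Every AE after it is treatment-emergent. SAP 4.5.1 applies a 5% display cut-off to the whole population.

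**Baselines.** SAP 3.2 sets the safety baseline at the last value before extension dosing. Protocol 3.1 lets the 812P306 end-of-study assessments serve as Visit 1 for Schedule A. The SAP efficacy baseline for those rolling over within 7 days is 812P306 Visit 2, before double-blind treatment. For those entering later it is extension Visit 1.

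**The concern.** Variable dosing explains why dose groups were dropped. It does not bear on prior exposure, which is fixed before the first extension dose and known from the 812P306 randomisation record.

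Two things are at stake, both under the primary safety objective.

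- **AE incidence.** An effect that began on SPN-812 during 812P306 is medical history in the extension. The same effect in a former placebo subject starts after extension dosing and is counted. A single percentage then describes neither starting the drug nor staying on it.
- **Change from baseline.** A Schedule A subject from the SPN-812 arm has a baseline on drug or shortly after it. A former placebo or de novo subject has a drug-free baseline. A pooled mean near zero could conceal movement in both groups.

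Early efficacy change is a lesser matter of interpretation. It contains the drug gain from 812P306 for some subjects, placebo response for others, and neither for those whose baseline is extension Visit 1.

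**Working it through.** The plan gives no AE rate, no group shares and no sample-size derivation (Protocol 7.10), so there is no figure to reproduce. All rates, shares and changes below are assumptions, except where a source is given.

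**1. Dilution of AE incidence.** Let s be the share already exposed in 812P306, p₁ the incidence in the newly exposed and p₂ the incidence in continuing subjects.

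Pooled = (1 − s)·p₁ + s·p₂, so shortfall = s·(p₁ − p₂).

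Assumed p₁ = 55%, p₂ = 35%:

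| s | Pooled | Shortfall |
|---|---|---|
| 30% | 0.7×55 + 0.3×35 = 49% | 6 points |
| 50% | 0.5×55 + 0.5×35 = 45% | 10 points |
| 70% | 0.3×55 + 0.7×35 = 41% | 14 points |

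A second illustration borrows the 812P302 rates of at least possibly related AEs (Protocol 1.2.3): 39.0% on 400 mg/day for p₁ and 19.2% on placebo for p₂. These are adolescent data and serve only to show scale. For s = 25%, 50% and 75% the pooled rate is 34.0%, 29.1% and 24.2%, a relative understatement of 13%, 25% and 38%. If p₂ = p₁ there is no dilution.

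**2. The 5% cut-off.** Assumed p₁ = 10%, p₂ = 3%. The pooled rate drops below 5% when s exceeds (10 − 5)/(10 − 3) = 71%; at s = 75% it is 4.8%. Such an event would leave the 5% displays. It should still appear in tables whose titles carry no cut-off, such as Table 4.2 ("Treatment-emergent Adverse Events by System Organ Class and Preferred Term - Safety Population").

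**3. Safety change from baseline.** Protocol 1.2.1 reports a slight heart rate increase after a single supratherapeutic dose. Assume −2 bpm in Schedule A subjects whose dose falls on entry and +2 bpm in the newly exposed. The pooled mean is s·(−2) + (1 − s)·(+2), that is +1.0, 0.0 and −1.0 bpm for s = 25%, 50% and 75%. The same mixing affects the QTcF change categories in SAP 4.5.5 and laboratory Tables 5.1.2 and 5.2.2.

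This does not apply to former SPN-812 subjects whose last 812P306 dose was already 200 mg and who roll over without a gap. Nor does it apply to Schedule B. Delayed rollovers have been past their last 812P306 visit for more than 7 days, against a half-life of about 7 hours (Protocol 1.2.1), and de novo subjects are untreated.

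**4. Efficacy change from baseline.** Under SAP 3.2, a Schedule A change equals the change during 812P306 plus the change since extension entry. Assume AISRS changes of −15 (drug) and −11 (placebo) in 812P306, then +2 and −3 to Visit 2. The tabulated changes are −13 and −14, with a 50:50 mean of −13.5. The signs agree. Opposite signs would require the whole 812P306 gain to be lost.

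**5. Size of a first-exposure column.** At the cap of 366, s = 25%, 50% or 75% leaves about 275, 183 or 92 newly exposed subjects. The 95% half-width at a 10% rate, 1.96·√(0.1×0.9/n), is 3.5, 4.3 or 6.1 points.

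**The case against.** The study is uncontrolled, has no power basis, and aims to collect long-term safety data. Neither document names risk in a new patient as an objective, and the placebo-controlled feeder study addresses initial exposure. Lower AE reporting by continuing subjects is plausible but undocumented. AE discontinuation on SPN-812 in the completed paediatric Phase 3 trials was only 1.2% to 5.6% (Protocol 1.2.3), so loss of intolerant subjects may be small. AE counts run to about 156 weeks, not only the starting weeks. De novo enrolment may be zero.

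Much of this stands. It makes the split a supplementary display and leaves the size open. It does not remove the point: dilution does not depend on dropout, because effects already under way at entry are not counted as new. Only the split can show whether the groups differ.

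A reader might go further and infer that the early efficacy means and Figures 1 to 7 average a worsening after step-down against an improvement on starting drug. The documents do not support that. SAP 3.2 measures Schedule A change from a pre-treatment baseline, and Protocol 6.1.4 anchors CGI-I there too. BRIEF-A, SDQ and AAQoL are not assessed at Visit 2 (Protocol 5.1.2), so Figures 5 to 7 should have no Visit 2 point. Doses may also change from Visit 2, so Visit 3 need not reflect 200 mg. Cancellation would arise under the baseline in Protocol 7.8 (last value before extension dosing), but the SAP supersedes it.

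**Conclusion.** The point holds for safety. Pooled AE percentages mix first exposure with continued use, and they understate first-exposure incidence if continuing subjects report fewer new events. That condition is reasonable but not documented. The 6 to 14 points rest entirely on the assumed 55% and 35% and on continuing shares of 30% to 70%; the true size cannot be found from the documents.

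Cancellation in laboratory, vital sign and ECG changes is possible, not demonstrated. It is confined to pooling Schedule A former SPN-812 subjects, where the drug effect at entry differs from that at the extension dose, with subjects who have a drug-free baseline.

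For efficacy, the pooled early means combine quantities of different meaning but probably the same sign. The change is worth making because it is cheap and serves the primary objective.

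**What to change.** In SAP 3.1, replace the single column with:

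- former SPN-812, rolling over within 7 days
- former SPN-812, entering by Schedule B (delayed or early-terminated)
- former placebo
- de novo, if any
- Total

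Use these columns in Tables 4.1 to 4.8, the exposure tables, the laboratory, vital sign and ECG tables (5.x, 6.x, 7.x), and the AISRS and CGI tables by visit. Take the arm from the 812P306 randomisation record. Separating the two former SPN-812 groups matters because only the first has an on-drug or just-off-drug baseline, and early terminators did not necessarily tolerate the drug. Show a TEAE in the 5% displays if it reaches 5% in any column.

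Footnote the efficacy baseline used in each column. Reconcile Protocol 7.8 with SAP 3.2 and state the efficacy baseline for de novo subjects, which SAP 3.2 does not give explicitly.

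The cost is SAP wording, programming and smaller columns, with Total retained. It needs no new data collection, only the 812P306 allocation once unblinded, and implies no change to dosing.
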